The specific aims of this pilot project are:

1) To evaluate the feasibility of studying whether implementation of family gardens paired with a nutrition intervention program in rural Guatemala will lead to improvements in maternal and child dietary diversity, child growth and household food insecurity compared to a nutrition intervention program alone.

2) Evaluate the implementation of the intervention through the Reach Effectiveness Adoption Implementation Maintenance (RE-AIM) framework.

We hypothesize that by augmenting a standard nutrition intervention with improved household food access through a garden intervention, child growth, dietary diversity and food security will improve compared to outcomes with the nutrition intervention alone.

2. Background

Children in Guatemala are at high nutritional risk, with a 47% prevalence of stunting (chronic malnutrition) and low full coverage with vitamin A supplements (UNICEF 2016). Only half of Guatemalan children receive a minimum acceptable diet (according to World Health Organization criteria measuring dietary diversity and meal frequency) from 6-23 months (UNICEF 2016). The indigenous Mayan population is disproportionately affected by poverty, food insecurity and malnutrition, with the prevalence of chronic malnutrition reaching as high as 70% in rural areas.

Wuqu' Kawoq/Maya Health Alliance (MHA) has conducted several studies to determine what nutrition interventions really work to prevent and treat chronic malnutrition. As a result of these studies, MHA established a home-based nutrition program whose goal is catch-up growth, improvement of minimum dietary diversity, minimum meal frequency, and minimum acceptable diet and increased caregiver knowledge. In a 50-child pilot, this intervention resulted in a mean change in height for age Z score (HAZ) from -3.67 ± 0.99 to -3.37 ± 0.89 over 6 months and an increase from 15-21% on minimum acceptable diet. In a subsequent RCT of this intervention, a trend toward improved growth at 6 months was observed, although the change was not statistically significant. However, minimum dietary diversity and minimum acceptable diet both improved significantly (risk difference 16.9 and 15.9%, respectively). The intervention also resulted in improved daily intake of legumes, eggs, and vitamin A rich fruits and vegetables (risk difference 16.5, 10.4, 12.7% respectively) (Martinez et al, 2018).

Agriculture is a major economic activity in Guatemala, with 70% of families working in this sector. Family agriculture has many obstacles, including lack of access to land and the expansion of cash crop (e.g., sugar cane, African palm) plantations. Most of the food that is grown locally is exported, rather than being used for local consumption.

Public and private organizations in Guatemala have worked to promote the production of food for consumption. However, very few of them have measured the impact of agricultural initiatives on nutritional status. Moreover, this is the first study in North Tecpán to evaluate the potential impact that adding a home food production (for

PROTOCOL TITLE:

Evaluating a family-based nutrition and garden intervention in rural Guatemala

consumption) component to a health-oriented nutrition program can have on maternal and child diet quality and nutritional status and household food security.

3. Study Design

This is a quasi-experimental study with an intervention group and a nonrandomly selected control (standard care) group.

- The *standard-of-care group* will consist of subjects recruited from Maya Health Alliance's nutrition program in prioritized communities of *North Tecpán, Chimaltenango, Guatemala*. Subjects in the standard care group will receive the current standard child nutrition care (growth monitoring, deworming medication, micronutrient supplementation, nutrition education classes and home visits).
- The *intervention group* will consist of subjects recruited from MHA's nutrition program in prioritized communities of *San Andrés Semetabaj, Sololá, Guatemala*. Subjects in the intervention group will receive the standard child nutrition care plus an additional agriculture component (agriculture education classes, supplies to build a home garden near the family home and on-going agricultural support).

A quasi-experimental design was selected because it was determined that household level randomization would be culturally and logistically difficult.

Both sites are rural. The intervention and control communities are 90 minutes apart by car and have similar prevalence of chronic malnutrition in children and similar sociodemographic characteristics (education levels, economic activity, health services, school access and food access).

In addition to the primary study endpoints (defined below), we will use the RE-AIM framework (Glasgow 1999) to evaluate the implementation of the intervention at the caregiver, provider and community levels. Broadly, the five elements of RE-AIM are: reach, effectiveness, adoption, implementation and maintenance. For each element, a variety of factors affecting implementation will be assessed. A select number of constructs from the Consolidated Framework for Implementation Research (CFIR) (Damschroder 2013) will also be considered as implementation factors within the RE-AIM framework. Data for this implementation analysis will be gathered through program documentation and auditing, home visit surveys, focus groups with participants, key informant interviews and semi-structured community interviews. More details about the RE-AIM framework for this study, the implementation factors to be assessed and the instruments for assessing them are outlined in Appendix J.

4. Inclusion and Exclusion Criteria

The study involves enrollment of subjects into an add-on gardening intervention who are already participating in an intensive standard-of-care nutrition intervention by MHA staff. Therefore, clinical staff (community health workers) at MHA who run that nutrition intervention will ascertain initial interest in participation in this study from their clients enrolled in the nutrition intervention. Subjects will be approached in their homes to discuss potential participation in the study.

PROTOCOL TITLE:

Evaluating a family-based nutrition and garden intervention in rural Guatemala

If clients express initial interest, the community health worker will provide that family's contact information to a study nurse, who is trained in human subject's research ethics and is a native speaker of Kaqchikel, the language spoken by the majority of the potential research subjects. This nurse will then conduct a home visit to potential subjects to explain the proposed research activities in more detail. If the family agrees to participate, then the nurse will administer the consent process and enroll them in the study.

Inclusion criteria are:

- Children who are already scheduled to be enrolled in MHA's intensive home-based nutrition program (non-investigational, standard of care) who are 6-24 months of age at the time of enrollment with a height-for-age Z scores of ≤ -2 – Households of children with height-for-age Z scores of ≤ -2.5 will be prioritized.
- At least one caregiver willing to provide written informed consent
- Caregiver of a child enrolled in the study, including women who may be pregnant
- Planned residence in the study area for the next 18 months

Exclusion criteria are:

- Children with acute malnutrition (weight for length Z scores of ≤ -2.0)
- Children with a severe medical illness that affects growth (e.g., heart disease, kidney disease, genetic condition) as determined by a MHA/Wuqu' Kawoq staff physician.
- Caregivers with cognitive impairments that prevent them from being able to provide informed consent

Children who are ineligible for enrollment in the research study will receive standard care (the home-based nutrition intervention) from MHA.

5. Number of Subjects

The study will enroll 140 children and their primary caregivers into two study groups: standard-of-care (n=70 children and 70 caregivers) and intervention (n=70 children and 70 caregivers).

6. Study Timelines

Five to ten families per month will be enrolled into the study from each study community. We anticipate that recruitment will take ~7-14 months.

The research team will have contact with enrolled participants over the course of 18 months. The primary study data collection time points will be at 0 months (enrollment), 6 months (end of standard of care/nutrition intervention), 12 months, and 18 months. It is anticipated that each of these study data collection visits will last approximately 1 hour,

PROTOCOL TITLE:

Evaluating a family-based nutrition and garden intervention in rural Guatemala

for a total of 4 hours. In addition to that, for the *intervention group only*, data will be collected at the first monthly agricultural home visit and at one additional agricultural home visit approximately 4 months thereafter. Each of these agricultural home visits will last approximately 1 hour for a total of an additional 2 hours. Combined, the total data collection time for the participant in the *intervention* group will be 6 hours.

The duration of the study interactions with the children and their caregivers is as follows:

- Standard child nutrition care (received by both groups) will last 6 months and will include nutrition classes for 5 weeks and one home visit a month. Standard nutrition care will involve approximately 16 hours of contact with MHA clinical personnel.
- The add-on agricultural/garden intervention (received by the intervention group only) will last 8 months and will include monthly agricultural classes and monthly home visits. The agricultural/garden intervention will involve approximately 16 hours of contact with MHA agricultural personnel, in addition to the time dedicated to the standard nutrition intervention.

A select number of participants (approximately 10) in the *intervention group* only will be asked to participate in one of two focus groups, approximately 90 minutes in length, between 6 and 9 months after the first enrollment. Participation in the focus groups will be fully voluntary and will not have any impact on the services or benefits received by the participants.

A small number of community leaders and Wuqu' Kawoq staff will be asked to participate in interviews, approximately 90 minutes in length, between 6 and 9 months after the first enrollment. Participation in the interviews will be fully voluntary.

The expected total duration of the study is approximately 3 years from the date of IRB approval.

7. Study Endpoints

The primary endpoints of this study are changes in the prevalence of:

- *Adequate diet quality*, as assessed by the World Health Organization (WHO) Infant and Young Child Feeding Indicators (IYCFI) (WHO, 2007) minimum dietary diversity, minimum meal frequency, minimum acceptable diet) for children and the Minimum Dietary Diversity for Women (MDD-W) indicator for caregivers. (FAO 2016)
- *Household food insecurity*, as assessed by the Global Food Insecurity Experience Scale (household referenced) (FAO 2017)

Secondary endpoints of the study include changes in: child length-for-age Z-score; child weight-for-age Z-score; child weight-for-length Z-score; child prevalence of stunting, wasting and underweight; and household total crop species diversity.

PROTOCOL TITLE:

Evaluating a family-based nutrition and garden intervention in rural Guatemala

This study involved no more than minimal risk, so no safety endpoints are specified.

8. Research Setting

The study will be conducted in prioritized communities of North Tecpán, Chimaltenango and San Andrés Semetabaj, Sololá (see additional details in **Section 3. Study Design**). These are rural Mayan language speaking communities where MHA has been working providing primary care and nutrition services for several years. MHA collaborates closely with multiple other NGOs as well as Ministry of Health staff in the region.

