- Monthly home visits from a study agronomist to provide assistance to build a garden near the family home and on-going support throughout the study

PROTOCOL TITLE:

Evaluating a family-based nutrition and garden intervention in rural Guatemala

Study data will be independently collected by a study nurse for all enrolled subjects at 0, 6, 12 and 18 months:

- Basic health history and demographics Appendix A
- Child weight and length/height Appendix B
- Household Quick Poverty Score (QPS) Appendix C
- Food Insecurity Experience Scale (household) Appendix D
- WHO Infant and Young Child Feeding indicators (child) Appendix E
- MDD-W Indicators (caregiver) Appendix F
- Agriculture Inventory Survey (household) to measure crop diversity and crop utilization Appendix G

Note that child weight and length and WHO IYCFI are already routinely collected as part of evaluation data for the standard-of-care nutrition services.

Additional data will be collected by the study agronomist for the *intervention group only* during the first agricultural home visit and at one additional agricultural home visit approximately 4 months thereafter:

- Agricultural Home Visit Baseline Survey (Baseline Agricultural Practices; Gardening Experience and Motivation) Appendix H
- Agricultural Home Visit Follow-up Survey (Adoption of Methods; Level of Home Garden Maintenance; Hours Worked in Home Garden) Appendix I

13. Data Analysis

Descriptive statistics for each group will be calculated using Stata (StataCorp, College Station, Texas). Family poverty scores will be calculated with a validated numerical scoring system commonly used in Guatemala. Changes in primary and secondary study outcomes will be compared between study groups using the chi-square test, paired t-tests (or the non-parametric equivalent) and linear and logistic regression as appropriate.

Within the intervention group, the rate of overall adoption will be compared descriptively across various demographic groups, and changes in primary and secondary outcomes will also be compared descriptively between adopters and non-adopters. Focus groups and interviews will be coded and analyzed thematically using select constructs from the Consolidated Framework for Implementation Research (CFIR) as a framework.

This is a pilot study to determine the feasibility of a garden intervention and to generate an initial effect size estimate for future, well-controlled studies. As such no formal power analysis will be performed.

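### Nothing aligns the enrolment calendars of the two sites, so a shared seasonal swing in diet or food security could enter the between-group change at months 6 and 18, though not at month 12

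*Combined protocol and SAP*

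**What the plan says.** Section 5 sets the groups at "standard-of-care (n=70 children and 70 caregivers) and intervention (n=70 children and 70 caregivers". Under Section 3 the standard-of-care families all come from North Tecpán and the intervention families all from San Andrés Semetabaj, without randomisation, so group and site are the same variable.

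Section 6 gives the pace, "Five to ten families per month will be enrolled into the study from each study community", and the duration, "We anticipate that recruitment will take ~7-14 months". It fixes the visits at "0 months (enrollment), 6 months (end of standard of care/nutrition intervention), 12 months, and 18 months"; Section 12 repeats that schedule for all enrolled subjects. The clock therefore starts at each family's own enrolment.

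The primary endpoints in Section 7 are changes in the prevalence of adequate diet quality and of household food insecurity. Section 13 begins its comparison with "Changes in primary and secondary study outcomes will be compared between study groups using the chi-square test, paired t-tests"; the sentence goes on to allow a non-parametric equivalent and linear and logistic regression as appropriate. No covariate is named. The supplied text gives no start date for either site, no rule that the sites recruit over the same months, and no mention of season.

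**The concern.** Diet and food supply in a farming population may well vary over the year. A visit 6 or 18 months after enrolment falls half a year away from the baseline season; a visit at 12 months falls in the same season. Each family's change at months 6 and 18 therefore carries a seasonal component that depends on the month of enrolment.

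That component cancels between groups only if the two sites have the same distribution of enrolment months. Since group equals site and allocation is not random, nothing in the design produces that match. Section 13 describes the study as a pilot meant to yield an initial effect size for later studies, and that estimate is what a calendar mismatch would distort.

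**Working it through.** **The plan's own figure.** 70 families ÷ 10 per month = 7 months; 70 ÷ 5 = 14 months. This reproduces the stated duration with the rate read per site. The slow case also fits the roughly 3-year study: 14 + 18 = 32 months out of 36.

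**Model.** Assume no garden effect and one seasonal curve shared by both sites, S(t) = A·cos(2π(t − φ)/12). A is in percentage points of prevalence and φ is the time of the peak. The documents give neither, so A is set at 2.5, 5 and 10 and φ is moved over the whole year.

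- Month 6 or 18: S(t+6) = S(t+18) = −S(t), so a family enrolled at t has a seasonal change of −2S(t).
- Month 12: S(t+12) = S(t), so the change is 0.

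**Even enrolment over L months.** The site mean of S is a cosine centred at the middle of the period, with amplitude A·R(L), where R(L) = sin(πL/12)/(πL/12).

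- R(7) = 0.527
- R(10) = 0.191
- R(14) = −0.136

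**7 against 14 months, same start.** The mid-points are 3.5 and 7 months, which is 3.5 months or 105° apart. The worst-phase difference in change is 2A·√(0.527² + 0.136² + 2 × 0.527 × 0.136 × cos 105°) = 2A × 0.509 = 1.02A.

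**7 against 10 months, same start.** The mid-points are 1.5 months or 45° apart: 2A·√(0.527² + 0.191² − 2 × 0.527 × 0.191 × cos 45°) = 0.83A.

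**One-month start gap, both sites enrolling for 7 months.** 4A × 0.527 × sin 15° = 0.55A. If both take 14 months, it is 4A × 0.136 × sin 15° = 0.14A, so 0.55A is an upper figure.

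**Same start, rates varying by chance.** Each site's monthly count is drawn independently from 5 to 10 until 70 are enrolled. At the worst phase the mean absolute false difference is 0.28A and the 95th percentile is 0.57A.

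False between-group difference in change at month 6 or 18, worst phase, in percentage points:

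| Enrolment pattern | Multiple of A | A = 2.5 | A = 5 | A = 10 |
|---|---|---|---|---|
| Same start, same rate | 0 | 0 | 0 | 0 |
| Same start, rates vary (mean) | 0.28 | 0.7 | 1.4 | 2.8 |
| Same start, rates vary (95th percentile) | 0.57 | 1.4 | 2.9 | 5.7 |
| One-month start gap, 7 months each | 0.55 | 1.4 | 2.7 | 5.5 |
| 7 v 10 months, same start | 0.83 | 2.1 | 4.1 | 8.3 |
| 7 v 14 months, same start | 1.02 | 2.5 | 5.1 | 10.2 |

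Averaged over all seasonal phases, each figure is multiplied by 2/π (about 0.64). At month 12 every row is 0.

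**Yardstick.** Section 2 quotes a risk difference of 16.9 points for minimum dietary diversity in an earlier trial of the nutrition programme. With A = 10, the mean chance-variation case is 2.8/16.9 = 17% of that, and the 7 v 14 case is 10.2/16.9 = 60%.

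**The case against.** Section 6 gives one range and one duration, and the ordinary reading is uncertainty about a shared recruitment period. A reader might infer that the plan expects one site to finish in 7 months and the other in 14, and so expects a bias of 5 to 10 points. The documents do not support that: 7 against 14 is the edge of what the text permits, and a figure of that size also needs an assumed swing of at least ±5 points and the worst phase. With a common start and chance variation the figure is about a quarter as large (0.28A against 1.02A).

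A reader might also infer that the planned analysis cannot handle season. It can: Section 13 includes regression, and regression can carry calendar terms. What stands is that none is named. Nor does the plan say that within-group 0-to-6-month changes will be read as programme effects; it compares changes between groups.

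Three further points have weight. The recall period of the food insecurity scale is in an appendix that was not supplied, and a long recall would damp a seasonal swing. Section 3 describes the sites as similar, including in food access; that makes a shared season plausible but does not align the months of measurement. Finally, this is a pilot, and a non-randomised two-site comparison carries other confounding that may be larger. That limits the weight of the point without removing it, because the correction is cheap.

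**Conclusion.** The concern holds in conditional form. If the enrolment calendars of the two sites differ, a shared seasonal swing enters the between-group change at months 6 and 18, and the plan neither prevents this nor adjusts for it. Month 12 is protected against a stable yearly cycle.

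For an assumed swing of ±2.5 to ±10 points, the false difference at the worst phase is about 1 to 3 points with a common start and chance variation in rates, and about 2.5 to 10 points at the 7 v 14 extreme. Direction is unknown. The figures rest on a sinusoidal season common to both sites, on outcomes that reflect the time of interview, and on an amplitude the documents do not supply. This is a worthwhile improvement to the pilot's effect-size estimate; it does not show that the estimate will be wrong.

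**What to change.** **Section 6.** Start both sites in the same month and aim for similar cumulative enrolment as recruitment proceeds. A strict month-by-month cap at the slower site's count is not advised. With rates varying independently between 5 and 10, such a cap lengthens recruitment in about 81% of simulated cases, by about one month on average.

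**Section 13.** Make the between-group comparisons by regression with annual sine and cosine terms for visit date. In a 6-month or 18-month change model one pair is enough, because the baseline terms are the same with opposite sign. Report the 0-to-12-month change as a season-matched sensitivity contrast. State its limit: Section 2 describes the child diet indicator for ages 6 to 23 months, so a child enrolled at 12 months or older has passed that range by month 12. The caregiver and household outcomes do not have this limit.

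**Cost.** Two model terms, a small loss of precision, and some coordination of the start. The adjustment is weaker the less the site calendars overlap, which is why the common start matters and must be settled before recruitment. Neither step removes a seasonal pattern that differs between the sites, or a one-off shock in a particular year; such a shock could affect month 12 as well.

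### At an on-schedule month-18 visit no child is aged 6-23 months, the only age span the documents attach to the WHO diet criteria; Sections 7 and 13 give no scoring rule from 24 months and no age term

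*Combined protocol and SAP*

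**What the plan says.** Section 7 (Study Endpoints) opens with "The primary endpoints of this study are changes in the prevalence of" and lists adequate diet quality, for children "as assessed by the World Health Organization (WHO) Infant and Young Child Feeding Indicators (IYCFI) (WHO, 2007) minimum dietary diversity, minimum meal frequency" and minimum acceptable diet. With the women's dietary diversity indicator and the household food insecurity scale, that makes five primary indicators, three of them on the child's diet. Section 7 gives no age limit, no rule for older children and no primary time point.

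Section 4 admits children "who are 6-24 months of age at the time of enrollment". Section 6 sets the schedule: "data collection time points will be at 0 months (enrollment), 6 months (end of standard of care/nutrition intervention), 12 months, and 18 months". Section 12 applies it to everyone: "Study data will be independently collected by a study nurse for all enrolled subjects at 0, 6, 12 and 18 months". The child feeding form is Appendix E, which is not in the supplied text.

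The one age span attached to the WHO diet criteria is in Section 2 (Background), in a national statistic on minimum acceptable diet: "according to World Health Organization criteria measuring dietary diversity and meal frequency) from 6-23 months".

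Section 3 describes the design: "This is a quasi-experimental study with an intervention group and a nonrandomly selected control (standard care) group". Section 13 compares changes between groups by chi-square test, paired t-tests or a non-parametric equivalent, and linear or logistic regression where suitable. It names no covariate. It also says that the pilot is meant to yield a first effect size for later studies.

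**The concern.** The children age by 18 months during follow-up, while the span stated for the diet criteria ends at 23 months. If that span governs the study's own indicators, the month-18 child result would carry a WHO label with no child in the labelled range. The month-6 and month-12 results would combine children inside and outside it. An analyst could then drop the older children, score them with extended cut-offs, or do some of each. These choices give different denominators and different endpoints.

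The second issue is comparability. Nothing in a two-community design balances entry age. If entry ages differ between the communities and prevalence changes with age in a non-linear way, the two groups would show different changes without any garden effect, and an analysis with no age term could read that as a garden effect. The estimate is meant to inform later studies, so its definition should be fixed in advance.

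**Working it through.** **Inputs.** Entry age 6-24 months (Section 4); visits at 0, 6, 12 and 18 months for all subjects (Sections 6 and 12); 140 children, 70 per group (Section 5); span 6-23 months, read as completed months, so below 24.0 (Section 2). The plan states no figure on this point to reproduce. It gives no entry-age distribution, so every share below except the month-18 zero rests on an assumed one.

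**Step 1. Age at each visit.** Age at visit = entry age + visit month. A child is in span if entry age < 24 − visit month. With x = (24 − visit month − 6)/18, the share in span is x for uniform entry on 6-24 months, 1 − (1 − x)² for entry skewed young (Beta(1,2), mean 12 months), and x² for entry skewed old (Beta(2,1), mean 18 months).

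| Visit (month) | Age range (months) | Entry age needed | Uniform | Skewed young | Skewed old |
|---|---|---|---|---|---|
| 0 | 6-24 | < 24 | 100% | 100% | 100% |
| 6 | 12-30 | < 18 | 12/18 = 67% | 89% | 44% |
| 12 | 18-36 | < 12 | 6/18 = 33% | 56% | 11% |
| 18 | 24-42 | < 6 (not eligible) | 0% | 0% | 0% |

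If 24 months means up to 24.99, uniform shares are 18/19 = 95%, 12/19 = 63%, 6/19 = 32% and 0%. About 5% of children, or 4 per group, are then out of span at enrolment.

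**Step 2. Child-visits out of span.** Planned: 140 × 4 = 560.
- Month 18 alone, under any entry-age distribution: 140 of 560 = 25%.
- Uniform: 140 × (0 + 1/3 + 2/3 + 1) = 280 (50%).
- Skewed young: 140 × (0 + 1/9 + 4/9 + 1) = 218 (39%).
- Skewed old: 140 × (0 + 5/9 + 8/9 + 1) = 342 (61%).

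**Step 3. Precision if only in-span children are used.** 95% half-width for a risk difference = 1.96 × √(2p(1 − p)/n), ignoring dropout and clustering by community. Per-group n under uniform entry is 70, then 70 × 0.667 = 46.7 at month 6 and 70 × 0.333 = 23.3 at month 12.
- p = 50%: 16.6, 20.3 and 28.7 points.
- p = 20%: 13.3, 16.2 and 23.0 points.

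A WHO-labelled, in-range result is therefore suitable only as a description.

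**Step 4. When age would bias the comparison.** Let p(a) be prevalence at age a with no garden effect. A group's expected change to visit t is the average of p(a + t) − p(a) over its entry ages.
- If p(a) = c + ba, every child's expected change is bt, so the between-group difference is zero whatever the entry ages.
- If the two entry-age distributions match, the difference is also zero.
- Otherwise it need not be zero.

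The documents give neither p(a) nor entry ages, so no size can be calculated.

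**Step 5. Precision cost of an age term.** In an illustrative simulation (70 per group, four visits, latent within-child correlation 0.3, no garden effect, piecewise-linear age), the SD of the month-18 group-by-visit estimate was 10.4 points unadjusted and 10.5 adjusted with matched entry ages. With a 3-month gap in mean entry age it was 10.5-10.7 and 11.1-11.3. The SD ratio over months 6, 12 and 18 was 1.00-1.06. A second simulation, with assumed prevalence flat at 50% or trending over 20-60% or 10-50%, gave ratios of 0.98-1.04 for gaps of 0-3 months and 1.07-1.16 for a 6-month gap. Where it assumed both an age gap and a rising trend, adjustment removed the resulting bias.

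**The case against.** The strongest reply is that the premise is not established. The 6-23 month span appears once, describing whom a national statistic covers. Section 7 defines the endpoint by citing a WHO source, not by that span. A scoring rule would most naturally sit in Appendix E, and Section 12 suggests that practice already exists: "Note that child weight and length and WHO IYCFI are already routinely collected as part of evaluation data for the standard-of-care nutrition services". Both groups share the same age criterion and schedule, so ageing is common to both. Section 13's regression could include age. The study is a pilot with no power analysis and no primary time point, so month 18 is not the decisive visit. No visit window is given either: a visit one month early would bring 1/18 = 6% of children (about 8 of 140, uniform entry) back under 24 months.

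Much of this stands, and it rules out three stronger conclusions that a reader might draw:
- That at least 140 endpoint values are invalid. The count is of child-visits outside a background span, and whether that span binds the endpoint is not stated.
- That the plan has no scoring rule. Only Sections 7 and 13 can be said to be silent, because Appendix E has not been seen.
- That the garden effect will be biased. That needs both an entry-age difference and a non-linear trend, and the documents show neither.

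The reply does not remove the point. Section 7 offers no other span. Permitting regression does not commit the analyst to an age term. A pilot meant to supply an effect size still needs a defined endpoint.

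**Conclusion.** The point holds conditionally and should be fixed. What needs no entry-age assumption is that, at on-schedule visits, 0 of 140 children are within 6-23 months at month 18, and that Sections 7 and 13 state neither a scoring rule from 24 months nor an age term. Children enrolled at 18 months or older are also outside the span at month 6, and those enrolled at 12 months or older at month 12. The in-span shares of 67% and 33% rest on uniform entry; the skewed cases give 44-89% and 11-56%.

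If the span governs the endpoint, three of the five primary indicators are affected: the month-18 child result is not the WHO indicator, and the month-6 and month-12 results are mixtures. The women's diet, food insecurity and growth endpoints are not touched by this span. A between-group comparison of all children remains possible. The missing age term is a weakness of the written analysis, but no size of bias is claimed.

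**What to change.** 1. **Section 7.** Check Appendix E for a scoring rule from 24 months. If there is one, cite it. If not, state one fixed prevalence rule for all three child indicators and apply it to every child at every visit. Either way, report WHO-labelled prevalence only for children aged 6-23 months at the visit, with its denominator, as descriptive, and label results from 24 months as adapted. A food-group count should not replace the primary endpoint: it is not a prevalence, and it covers neither meal frequency nor acceptable diet.

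2. **Section 13.** Compare change between groups with a regression on group, visit, group-by-visit interaction and child age at the visit (non-linear terms allowed), allowing for repeated measures within child. On the prevalence-difference scale the interaction is the between-group difference in change, so the stated endpoint is kept. State that this does not account for clustering among the several communities in each arm, or for other differences between the two areas.

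**Cost.** A text amendment, with no new visits. Age at each visit is already needed for the growth Z-scores, so step 2 needs no new data. Step 1 needs none if Appendix E records foods and meals at any age, which must be checked. The all-children results at 12 and 18 months will not be directly comparable with published WHO figures. The model assumes a common age effect in both groups. In illustrative simulation, intervals widen by about 0-6% for entry-age gaps up to 3 months and by about 7-16% for a 6-month gap.
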